## **Background and Rationale**

Bladder cancer remains a significant health burden globally, with non-muscle invasive bladder cancer (NMIBC) representing a majority of cases. Intravesical Bacillus Calmette-Guerin (BCG) therapy is widely accepted as a standard adjuvant treatment for intermediate- and high-risk NMIBC. However, the comparative efficacy and safety profiles of different BCG substrains remain unclear. This study aims to address this gap by comparing the RIVM and Russian BCG substrains.

## **Objectives**

- **Primary Objective:** To evaluate the efficacy of BCG RIVM versus BCG Russian substrains in terms of recurrence-free survival (RFS) and progression-free survival (PFS).
- **Secondary Objective:** To compare the safety and adverse event profiles between the two substrains.

## **Study Design**

This is a randomized prospective clinical trial conducted at Ankara University Ibni Sina Hospital from January 2019 to December 2022.

## **Inclusion Criteria**

1. Age  $\geq 18$  years.
2. Histopathologically confirmed NMIBC (Ta, T1, or CIS).
3. Intermediate-, high-, or very high-risk classification based on EAU guidelines.
4. No prior BCG therapy within the last year.
5. No evidence of upper urinary tract carcinoma or distant metastases.
6. Minimum follow-up period of 12 months.

## **Exclusion Criteria**

1. Inadequate BCG therapy (fewer than 5 induction doses or fewer than 2 maintenance doses).
2. Follow-up period less than 12 months.
3. Use of multiple BCG strains.
4. Previous history of BCG therapy.

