### Intervention

Both groups received an induction course of six weekly intravesical BCG instillations, followed by maintenance therapy as per risk stratification protocols.

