### Outcome Measures

- **Primary Outcomes:**
  - Recurrence-free survival (RFS): Time from randomization to tumor recurrence.
  - Progression-free survival (PFS): Time from randomization to disease progression.
- **Secondary Outcomes:**
  - Adverse events: Assessed using the National Cancer Institute Common Terminology Criteria for Adverse Events (CTCAE).

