### Results Summary

- A total of 125 patients were analyzed: 61 in the BCG RIVM group and 64 in the BCG Russian group.
- No significant difference in RFS or PFS between the groups.
- Adverse event rates were comparable.

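### The minimum-dose exclusion can be applied only after randomisation and no RFS, PFS or safety population is named, so a reader cannot tell whether the analysed groups are the randomised groups

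*Combined protocol and SAP*

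**What the plan says.** Exclusion Criteria, item 1, removes patients for "Inadequate BCG therapy (fewer than 5 induction doses or fewer than 2 maintenance doses". The Intervention section describes the trial treatment in the same terms: "Both groups received an induction course of six weekly intravesical BCG instillations, followed by maintenance therapy as per risk stratification protocols".

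Three other entries bear on who is analysed:

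- Exclusion Criteria, item 2: "Follow-up period less than 12 months", mirrored in Inclusion Criteria, item 6: "Minimum follow-up period of 12 months".
- Exclusion Criteria, item 3: "Use of multiple BCG strains", with no time period attached.
- Study Design: the trial ran "from January 2019 to December 2022". No last-enrolment or data cut-off date is given.

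Outcome Measures starts the clock at randomisation: "Recurrence-free survival (RFS): Time from randomization to tumor recurrence". PFS has the same origin. Statistical Analysis lists Kaplan-Meier, chi-square and Cox methods and a 0.05 threshold, but no analysis population for efficacy or safety.

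The Randomization section gives 61 patients on RIVM and 64 on Russian. The Results Summary gives the same two numbers as analysed, finds no significant RFS or PFS difference, and states "Adverse event rates were comparable". The Conclusion treats the two substrains as alike in efficacy and safety.

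**The concern.** A patient who has been randomised but stops BCG before the second maintenance dose fails item 1. The reasons for stopping include toxicity, recurrence, progression and death, which are the trial's outcomes or closely tied to them. With the clock starting at randomisation, removing such patients drops outcomes from the arm in which they occurred. The selection is partial: a patient who recurs early but still satisfies the rules is kept.

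At stake is whether the comparison retains the protection of randomisation. Removing early failures makes RFS and PFS look too good. Removing only event-free patients lost before 12 months makes them look too poor. Removal unrelated to outcome does no harm. Removing toxicity stops lowers the reported adverse-event rates. Unequal removal between arms can create or hide a difference. No exclusion counts are given, so a reader cannot judge which of these, if any, applies.

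**Working it through.** **1. Counts.** 61 + 64 = 125, which reproduces the analysed total and equals the total given as randomised. At face value there was no loss. If 125 were instead a count after exclusion of a fraction d (assumed), the number randomised would be 125/(1 − d), rounded up: 132, 139, 157 or 179 for d = 5%, 10%, 20% or 30%. If 125 were truly randomised and each patient had an independent exclusion risk of 1%, 2% or 5% (assumed), the chance of no exclusions is (1 − d)^125 = 28%, 8% or 0.2%. This does not show which reading is true.

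**2. When each rule can be applied.**

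- *Dose rule:* the wording matches the Intervention section, so trial BCG is the natural reading. It is known only after randomisation.
- *12-month rule:* attained follow-up is known only later. Potential follow-up (enrolled at least 12 months before cut-off) depends on calendar date alone and would not remove early deaths or losses. The plan does not say which is meant.
- *Strain rule:* undated. If any earlier BCG is barred (Exclusion Criteria, item 4), it can bite only through trial BCG. If only BCG in the last year is barred (Inclusion Criteria, item 4), it could refer to older courses.

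**3. Single-arm RFS.** All inputs are assumed: constant hazard, true 24-month RFS S = 0.60, so λ = −ln(0.60)/24. Maintenance timing is not given, so the cut-off c is varied.

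Removing every failure before month c gives S/S(c) = 0.60^(1 − c/24), an upper bound for that cut-off:

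| c (months) | Reported RFS |
|---|---|
| 3 | 64% |
| 6 | 68% |
| 9 | 73% |
| 12 | 77% |

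Removing only patients lost event-free before month 12, with independent loss L by month 12 and g = −ln(1 − L)/12: let ps = exp(−12(λ + g)) and pe = λ/(λ + g) × (1 − ps). Reported RFS = ps/(pe + ps) × exp(−12λ). For L = 10%, 20% and 30% this is 59%, 58% and 57%.

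Removing the same fraction of early failures and of everyone else leaves 60%.

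**4. The comparison between arms.** Under constant hazards, true 24-month RFS of 60% v 50% is a hazard ratio of ln(0.50)/ln(0.60) = 1.357. Removing all failures before month 6 from both arms leaves it at 1.357.

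A log-rank simulation (4,000 runs per scenario, 61 v 64 analysed, two-sided 0.05, uniform censoring from 12 to 48 months, failures before month 6 eligible for removal) gave:

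| Scenario | Removed, arm A v B | Apparent HR, B v A | Rejection rate |
|---|---|---|---|
| True HR 1, 24-month recurrence 20–40% | 0 v 0 | about 1.00 | about 5–6% |
| Same | 0.5 v 0.5 | about 1.00 | about 5% |
| Same | 0.8 v 0.2 | 1.17–1.20 | 6.5–10% |
| True HR 2, 30% recurrence in arm A | 0 v 0 | 1.99 | 75% |
| Same | 0.5 v 0.5 | 1.97 | 69% |
| Same | 1 v 1 | 1.97 | 66% |

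The analysed numbers are held at 61 and 64, so the power loss is what follows if those are counts after exclusion.

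**5. Safety.** Assume true rates p of 20% v 10%, with the same fraction f of affected patients removed in each arm and no unaffected patients removed. Reported rate = p(1 − f)/(1 − pf).

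| f | Rates | Difference (points) | Odds ratio |
|---|---|---|---|
| 0 | 20% v 10% | 10 | 2.25 |
| 0.2 | 16.7% v 8.2% | 8.5 | 2.25 |
| 0.4 | 13.0% v 6.3% | 6.8 | 2.25 |
| 0.6 | 9.1% v 4.3% | 4.8 | 2.25 |

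**The case against.** The strongest reply is that the documents show no exclusion at all: everyone counted as randomised is counted as analysed. That stands as far as it goes. A reader might infer from the identical counts that patients were removed and the totals restated, but the documents do not support this. Nobody may have met the rules, patients who met them may have been kept, or 61 and 64 may be counts after exclusion.

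A second reply is that the objective is comparative, and equal removal largely spares the comparison. This also stands for the hazard ratio and for the adverse-event odds ratio. The single-arm RFS figures therefore do not measure bias in the strain comparison; that needs unequal removal. What remains under equal removal is lost power and a smaller absolute safety difference, both relevant to a finding of no difference.

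Third, it is tempting to say that all the rules plainly depend on later events. Only the dose rule supports that, and on its most natural reading rather than by explicit statement. The 12-month rule is undefined, and the inference for the strain rule depends on which of two conflicting prior-BCG criteria governs.

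**Conclusion.** The point holds as a defect in the plan. The dose rule, read with the Intervention section, selects on what happens after randomisation, while the endpoints run from randomisation and no population is named. The 12-month rule has the same defect if attained follow-up is meant, and the strain rule may have it. The need to fix this rests on the missing population and participant flow, not on any demonstrated bias; actual bias may be nil.

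The possible size depends wholly on assumed inputs. Single-arm RFS could be several points too high or a few points too low, with the upper bound sensitive to the cut-off chosen. An apparent hazard ratio near 1.2 with no true difference requires strongly unequal removal. A reader might conclude that the finding of similarity is therefore wrong. The documents do not support that; they only leave it unverifiable whether the finding rests on the randomised groups.

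**What to change.** 1. In Randomization and Results Summary, report the numbers randomised and excluded per arm with reasons, or state that nobody was excluded.
2. In Statistical Analysis, make the primary RFS and PFS comparisons include all randomised patients in the arm assigned, whatever their dose count, strain switching or length of follow-up. Censor patients who are alive and event-free at their last assessment. State separately how deaths without recurrence or progression are handled; the outcome definitions do not count them as events, and the censoring rule should not settle this by default.
3. Define the safety set as all patients with at least one instillation, by strain received, and report how many switched and how they are classified.
4. Say whether the 12-month rule means attained or potential follow-up, and give the last-enrolment and data cut-off dates.
5. Keep the dose-, strain- and follow-up-restricted set as a labelled per-protocol sensitivity analysis.
6. Because results are already reported, label any newly chosen population post hoc. If excluded patients' data cannot be recovered, label the result per-protocol and qualify the Conclusion.

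**Cost.** If nobody was excluded, this is wording and a flow count. If anyone was, a re-analysis is needed, and the documents do not say whether those patients' records are usable. The estimate becomes the effect of assignment rather than of an adequate course, and some restored patients will have short follow-up.

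The conflict between Inclusion Criteria, item 4, and Exclusion Criteria, item 4, on prior BCG is a separate point; those entries must be reconciled.

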## Methods

### Randomization

Patients were randomly assigned to receive either BCG RIVM (n=61) or BCG Russian (n=64).

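### The dose and follow-up exclusions have no toxicity exception and no safety population is defined, so, applied as written, they drop patients whose adverse event ended treatment below a dose minimum

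*Combined protocol and SAP*

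**What the plan says.** The Exclusion Criteria list inadequate BCG therapy, defined as "fewer than 5 induction doses or fewer than 2 maintenance doses", and, as a separate item, "Follow-up period less than 12 months". The Inclusion Criteria state the second condition again: "Minimum follow-up period of 12 months". No exception is given for patients who stopped because of an adverse event.

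The Intervention section describes "an induction course of six weekly intravesical BCG instillations, followed by maintenance therapy". The dose counts can therefore be known only once treatment is under way.

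Comparing safety is the secondary objective, and Outcome Measures names CTCAE-assessed adverse events as the secondary outcome. Neither section names the patients to be counted. Statistical Analysis gives chi-square tests for categorical variables without a denominator. No section defines a safety, as-treated or intention-to-treat set.

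Randomization gives 61 RIVM and 64 Russian patients. The Results Summary states "A total of 125 patients were analyzed: 61 in the BCG RIVM group and 64 in the BCG Russian group" and "Adverse event rates were comparable", with no adverse event counts. The Conclusion extends similar safety to NMIBC treatment without restriction.

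**The concern.** These criteria are listed as eligibility rules, but they act as filters on what happens after treatment starts. A patient with a reaction severe enough to end treatment during induction or early maintenance is among those most relevant to a safety comparison, and that patient meets the exclusion.

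If the filter was used, the reported adverse event rates describe only patients who reached the dose and follow-up minimums. A difference between substrains in early stops for toxicity could not appear. Even equal early toxicity in both arms would leave the rates describing patients who tolerated the minimum course. The Conclusion, which supports choosing a substrain by availability and preference, carries no such limit.

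**Working it through.** **1. Who is removed and who stays, on the text.**

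| Patient | Applied as written |
|---|---|
| Stops for toxicity with fewer than 5 induction doses | Excluded |
| Stops for toxicity after induction with fewer than 2 maintenance doses | Excluded |
| Followed for under 12 months, for any reason | Excluded |
| Misses only the sixth induction dose, receives 2 maintenance doses, followed 12 months | Kept |
| Early adverse event but continues past both minimums, followed 12 months | Kept |
| Stops for toxicity after both minimums, followed 12 months | Kept |

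**2. Counts in the document.** 61 + 64 = 125, which matches the stated total. Randomized minus analyzed is 61 - 61 = 0 and 64 - 64 = 0. This fits three readings: no one met the criteria, the criteria were not enforced after randomization, or the counts under Randomization were taken after exclusion. The document does not say which.

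**3. Size on the specified outcome, overall adverse events.** No adverse event counts are given, so every count from here on is assumed. Differences are first arm minus second, with Newcombe 95% intervals and uncorrected chi-square P values. The assumed base is 18/61 (29.5%) versus 19/64 (29.7%).

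- Add back 6 versus 0 patients, all with events: (18+6)/(61+6) = 24/67 (35.8%) versus 19/64 (29.7%). The difference is 6.1 points (-9.8 to 21.6), P=0.45 (Fisher 0.46).
- The reverse, 0 versus 6: 18/61 versus 25/70, -6.2 points (-21.6 to 9.8), P=0.45.
- Add back 6 versus 0 patients without events, excluded for other reasons: 18/67 (26.9%) versus 19/64 (29.7%), -2.8 points (-18.0 to 12.4), P=0.72.

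With equal base rates from 5% to 70%, adding back 6 versus 0 patients with events never reaches P<0.05 (P=0.08 to 0.72). The smallest one-sided number removed that would give P<0.05 is:

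| Base rate | 5% | 10% | 20% | 30% | 50% | 70% |
|---|---|---|---|---|---|---|
| Chi-square | 8 | 10 | 15 | 19 | 30 | 46 |
| Fisher exact | 8 | 11 | 16 | 20 | 31 | 51 |

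**4. Size on discontinuation for toxicity below the minimums.** If the rule was applied, this count is 0 in both analyzed arms by construction. Fisher P is used because the smallest expected counts are below 5 (for example 2.9 for 6 versus 0).

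| Added back | Rates | Difference, points (95% CI) | Fisher P |
|---|---|---|---|
| 6 vs 0 | 6/67 vs 0/64 | 9.0 (1.5 to 18.2) | 0.028 |
| 5 vs 0 | 5/66 vs 0/64 | 7.6 (0.5 to 16.5) | 0.058 |
| 6 vs 2 | 6/67 vs 2/66 | 5.9 (-2.9 to 15.4) | 0.27 |
| 4 vs 4 | 4/65 vs 4/68 | 0.3 (-8.8 to 9.6) | 1.00 |

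**5. How a real difference could be hidden.** Let d be the share of randomized patients in an arm who stop for toxicity below a minimum, each counted as having the event, and r the event rate among those kept. The rate in all treated patients is p = d + (1 - d)r. With r = 5% in both arms and d = 5% versus 15%:

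- p = 0.05 + 0.95 × 0.05 = 9.8% versus 0.15 + 0.85 × 0.05 = 19.3%, a difference of 9.5 points.
- The analyzed difference is 0, because r is the same in both arms.
- The patients missing would be 61/0.95 - 61 ≈ 3 and 64/0.85 - 64 ≈ 11.

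With d fixed at 5% in one arm and running from 5% to 20% in the other, the hidden difference runs from 0 to 14.3 points at r = 5%, and from 0 to 13.5 points at r = 10%.

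**The case against.** The strongest reply is that no loss is shown. The randomized and analyzed counts agree, and at face value everyone randomized is in the safety comparison. The Intervention section says in the past tense that both groups received the six-week course, which weakly favors little early dropout. Nothing in the text favors the reading that the randomized counts were taken after exclusion. This stands as far as it goes: no removal is demonstrated. It does not settle the point, because the wording about the course is at group level and no exclusions are reported by arm or reason.

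A second reply is that the only calculation reaching significance uses discontinuation for toxicity, which the plan does not list as an outcome. It also needs a fully one-sided split, and 5 versus 0 already misses the threshold. That is fair. The calculation shows what the rule can hide, not what happened. On the specified outcome, a few removals would not overturn the reported result, although a non-significant P value does not itself establish similar safety.

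Two smaller points also stand. The plan names chi-square rather than Fisher tests, but the choice moves the removal thresholds only slightly. And no separate calculation is offered for the 12-month rule. Its effect is to discard adverse events already recorded in patients with shorter follow-up.

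**Conclusion.** The concern holds as a statement about the rule. Applied as written, the criteria remove patients whose adverse event ended treatment below a dose minimum, and no safety population brings them back. This is more than a missing detail, because following the stated rule selects on tolerance of treatment.

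Confidence is high on the text and on that conditional consequence, but not on any actual bias. The number removed is unknown and may be zero, and the direction could be either way. If a handful were removed, the overall adverse event comparison would probably still look comparable, while information on early stops for toxicity would be absent. These sizes rest entirely on assumed removal counts and base rates. The point should be fixed, since the Conclusion claims similar safety without limit and the reader cannot tell which patients it covers.

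**What to change.** 1. State by arm the numbers randomized, excluded and analyzed, with the reason for each exclusion: toxicity, other under-dosing, follow-up under 12 months, or multiple strains. If no one was excluded, or the criteria were not enforced after randomization, say so.
2. Define the safety population as all randomized patients with at least one instillation, grouped by first substrain received, with no minimum number of doses or length of follow-up. Grouping by first substrain is one convention among several; what matters is that it is stated.
3. Report adverse events on that set and base the safety conclusion on it. Report discontinuation for toxicity as well, labeled as added after the results were known.
4. If adverse event data for excluded patients were not kept, limit the safety statement in the Conclusion to patients who met the dose and follow-up minimums.

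The cost depends on what happened. If no one was excluded or the criteria were not enforced, it is one sentence. If patients were excluded and their data exist, it is revised analysis wording and re-run adverse event tables, and reported toxicity may move in either direction. If the data are gone, the set cannot be rebuilt and the remedy is a stated limitation with a narrower conclusion. No change to dosing or treatment rules is involved.

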## Methods

### Randomization

Patients were randomly assigned to receive either BCG RIVM (n=61) or BCG Russian (n=64).

### Intervention

Both groups received an induction course of six weekly intravesical BCG instillations, followed by maintenance therapy as per risk stratification protocols.

### Outcome Measures

- **Primary Outcomes:**
  - Recurrence-free survival (RFS): Time from randomization to tumor recurrence.
  - Progression-free survival (PFS): Time from randomization to disease progression.
- **Secondary Outcomes:**
  - Adverse events: Assessed using the National Cancer Institute Common Terminology Criteria for Adverse Events (CTCAE).

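### CIS that persists after induction is not an RFS event as written, and the minimum-dose exclusion can remove the same patients from the analysis

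*Combined protocol and SAP*

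**What the plan says.** Inclusion Criteria, item 2, admits "Histopathologically confirmed NMIBC (Ta, T1, or CIS"), so CIS is eligible. The document does not say how many patients had it.

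Outcome Measures names two primary outcomes: RFS, defined as "Time from randomization to tumor recurrence", and "Progression-free survival (PFS): Time from randomization to disease progression". Neither recurrence nor progression is defined, and persistent disease is not mentioned.

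Intervention states: "Both groups received an induction course of six weekly intravesical BCG instillations, followed by maintenance therapy as per risk stratification protocols". It describes no response assessment between induction and maintenance. Statistical Analysis names Kaplan-Meier and Cox methods but gives no censoring rule.

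Exclusion Criteria, item 1, removes "Inadequate BCG therapy (fewer than 5 induction doses or fewer than 2 maintenance doses"), with no exception for a patient who stopped because treatment had failed. Item 2 removes anyone with "Follow-up period less than 12 months". Both can be known only after treatment has begun.

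**The concern.** Recurrence presupposes a disease-free state. That is a workable event for papillary disease that has been resected. A patient with CIS may still have it at randomisation, and the first question is then whether BCG clears it. If it does not, treatment has failed, yet nothing has come back, and the RFS definition gives neither an event nor an event date.

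The dose exclusion bears on the same patients. A patient whose disease has cleared is more likely to reach two maintenance doses than one found to have persistent disease at the first check. The analysis set is therefore conditioned on something that follows randomisation and is linked to outcome.

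RFS carries the efficacy conclusion. Results Summary reports no significant RFS or PFS difference, and Conclusion reads this as similar efficacy. In CIS, clearance of existing disease is a direct measure of what a substrain does, so whether these failures are counted, and whether the patients are analysed at all, should be settled in writing.

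**Working it through.** **Following one patient through the text.** A patient with CIS is eligible (Inclusion Criteria, item 2) and completes induction, and CIS is still present. Under Outcome Measures there is no recurrence, hence no RFS event as written. From there:

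- If BCG continues to at least two maintenance doses, the patient stays in the analysis. No rule says whether or when the RFS clock stops.
- If BCG stops earlier, Exclusion Criteria, item 1, removes the patient.
- If the disease later progresses and the patient is still in the analysis, there may be a PFS event. Persistence at the same stage need not count as one.

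**Number affected.** The plan has no sample-size or event calculation to reproduce. Its one checkable sum agrees: 61 + 64 = 125, from Randomization and Results Summary. CIS share and persistence are not given, so both are assumed:

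- affected patients = 125 × CIS share × persistence
- low: 125 × 0.10 × 0.30 = 3.75, about 4
- high: 125 × 0.30 × 0.50 = 18.75, about 19
- a wider range of 5-30% CIS and 20-50% persistence gives 125 × 0.05 × 0.20 = 1.25, so about 1 to 19

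**Effect on the comparison.** This was checked by log-rank simulation. Everything except the arm sizes is an assumption: 61 vs 64 patients, follow-up uniform over 12-48 months, 35% two-year recurrence in the reference arm, and HR 0.6 for recurrence. Persistent CIS is either counted as an event at 3 months or censored there. Two cases were run: persistence of 50% in the reference arm vs 25% in the better arm (1,500 trials per row), and 40% in both arms (1,200 trials per row).

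| CIS share | Power, 50% vs 25%: counted / censored | Power, 40% in both: counted / censored | Estimated HR, 40% in both: counted / censored |
|---|---|---|---|
| 10% | 0.41 / 0.36 | 0.35 / 0.38 | 0.63 / about 0.60 |
| 20% | 0.47 / 0.33 | 0.30 / 0.36 | 0.66 / about 0.60 |
| 30% | 0.51 / 0.33 | 0.26 / 0.32 | 0.69 / about 0.60 |

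A repeat of both cases gave values within 0.03 of these power figures. The 0.03 gap at 10% CIS with equal persistence is therefore no larger than the variation between runs.

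In the first case, removing these patients instead of censoring them gave power of 0.36, 0.35 and 0.34, much the same as censoring.

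The reason for the reversal is simple. If clearance differs in the same direction as recurrence, counting persistence adds informative events. If clearance is equal, counting it adds events in a ratio near 1 and pulls the overall HR toward 1. Note that the 25% in the first case lies below the 30-50% range used for the head count.

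If the substrains differ only in CIS clearance (50% vs 25%), the HR is 0.94, 0.90 or 0.86 when persistence is counted and about 1.0 when it is censored. Power is only 0.06-0.08 and 0.04-0.06 respectively, so the estimate moves but the significance test would rarely change.

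**The case against.** The best reply is that the plan is silent here and does not prescribe a wrong rule. Recurrence is undefined, so the analysts may have counted persistent CIS as recurrence. That is possible, but the text does not say so, and two analysts working from it could report different event counts.

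Four stronger readings are tempting, and the documents do not support them:

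- *Persistent CIS is never a primary event.* PFS is also primary, and later progression could be captured there.
- *These patients are censored.* No censoring rule exists. Censoring in the simulation is one possible handling, not the plan's.
- *BCG failures in general are lost.* Disease that returns after clearing, papillary or CIS, is a recurrence and counts if the patient is in the analysis set. Only CIS that never clears is at issue.
- *Patients were in fact dropped.* Randomization says "Patients were randomly assigned to receive either BCG RIVM (n=61) or BCG Russian (n=64"), and the same 61 and 64 reappear as the analysed numbers. This neither shows exclusions nor rules them out, because the text does not say whether those counts precede or follow the exclusion criteria.

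It can also be said that the dose exclusion is a wider problem than CIS. That is right, and the remedy should therefore cover all randomised patients. It remains relevant here because, with no exception for failure, it can remove the very patients whom the endpoint leaves out.

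**Conclusion.** The point stands as a gap in the endpoint definition combined with a written, outcome-linked exclusion. CIS is enrolled, CIS that persists after induction is not an RFS event as written, and a patient with persistent CIS who stops BCG before two maintenance doses can leave the analysis.

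The scale is about 4 to 19 of 125 patients if CIS makes up 10-30% and persistence is 30-50%. Neither figure is in the documents.

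A reader might infer that the omission pushed the trial toward its finding of similar efficacy. That does not follow. The simulations show power lost by omission when clearance differs between the substrains (for example 0.47 to 0.33 at 20% CIS) and gained when clearance is equal (0.30 to 0.36). Without CIS counts and persistence by arm, neither the size nor the direction of any bias in the actual data can be stated. The change is worth making because the primary event should be determinate and should include clear treatment failure, not because a particular bias has been shown.

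**What to change.** 1. In Outcome Measures, define the RFS event as *first documented recurrence, or persistent CIS at the first post-induction assessment on record, whichever comes first*. State what that assessment is and use its date as the event date, since the plan schedules none. State the censoring rule as well.
2. Analyse every randomised patient in the assigned arm whatever number of doses was received, not only those with persistent CIS. Use the minimum-dose set as a sensitivity analysis only. Say whether 61 and 64 are counts before or after exclusions.
3. Report by arm the number with CIS and the number whose CIS persisted, so that clearance can be seen separately from later recurrence.
4. Add a sensitivity analysis of RFS limited to Ta/T1 patients without CIS. This shows how far the result depends on the persistence rule, including the dilution that occurs if clearance is equal.

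The cost is a few sentences, additional Kaplan-Meier and Cox runs, a review of post-induction findings in patients with CIS, and recovery of outcomes for any patients already excluded. Reported RFS will look slightly less favourable in both arms.
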